Rugby is contact sports that need good physical fitness skills and specific skills depending on the position played. The team that can quickly and efficiently communicate during a rugby game has a clear advantage. Thus, building good on-field communication habits make much easier for rugby players to work together. However, if the communication fails during rugby games, the prospect of success in offense and defense during rugby games will be greatly decreased (Gordon, 2005). Among Malaysian university rugby players, those who discontinued using mouthguard complaint that general discomfort and speech disturbance are the main barriers to compliance (Liew et al., 2014). The nuisance is largely due to their use of poorly-fitted stock or boil-and-bite mouthguards (Liew et al., 2014). In comparison, custom-fitted mouthguards were considered the best choice because of its ability to maintaining oral moistness and adaptation, hence causing less interference with respiration and speech, while improving comfort and limiting nauseating effect (Duarte-Pereira et al., 2008). However, limited availability and higher prices hinder its widespread use (Guevara et al., 2001).

To date, the intensity and duration of oral discomfort caused by mouthguard remain unclear, with no published study to evaluate speech performance that employed acoustic analysis and sonography. Hence, the aim of this research is to evaluate the impact of wearing mouthguards on the speech performance of the athletes.

2. Problem Statement

Rugby exposes players to increased risk of dental trauma. Thus, mouthguard use is often recommended. However, a mouthguard can affect speech. It is unclear to what extent speech performance improve over time.

Therefore, this project is intended to evaluate the impact of wearing mouthguards on the speech performance of the players. In addition, the effectiveness of custom-fitted mouthguards in the prevention of dental trauma could be evaluated.

3. Research Question

- i. Is there any difference in speech performances before (at baseline), immediately after, one-week after, one-month after and six-month after wearing a custom-fitted mouthguard?
- ii. Is there any difference in the level of oral impairment immediately after, one-week after, one-month after and six-month after wearing a custom-fitted mouthguard?
- iii. What is the incidence of traumatic dental injury among rugby players during the six-month period of wearing a custom-fitted mouthguard?

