The sample size was calculated using G*Power 3.1 software (available at <http://www.gpower.hhu.de/>). The assumptions was an effect size of 0.25 with a 5% margin of error. The power of the study 80% and there was a total of six repeated measurements. Correlation among the repeated measures was set at 0.5. This yielded a minimal sample size of 24. Considering that drop-outs are higher with long-term follow-up, the sample size was increased by 20% to $n = 30$.

Development of questionnaire to evaluate oral impairment

A questionnaire will be developed to evaluate any oral impairment that could be experienced by the subjects before and during the use of a mouthguard. The questionnaire will be divided into four parts: (i) demographic information such as gender, age, frequency and duration of playing, highest level of representation and experience wearing custom-fitted mouthguard, (ii) frequency of wearing mouthguard, (iii) problems arise during mouthguard use and (iv) general perception on mouthguard. All questions in part (ii), (iii) and (iv) will be formatted in a five-point Likert scale. The following ratings will be given for the different possible answers in part (ii) and part (iii) with a qualitatively ordinal character: “Never” = 1; “Rarely” = 2; “Sometimes” = 3; “Often” = 4; “Always” = 5. For part (iv), the possible responses were: “Strongly disagree” = 1; “Disagree” = 2; “Neutral” = 3; “Agree” = 4; “Strongly agree” = 5. The questionnaires will be printed in Malay, the national language of Malaysia.

This questionnaire set will be validated and pretested on 10 undergraduate dental students. The cognitive interview will be carried out while the students are completing the questionnaire. Face validity will be determined as the degree to which they agree that the items of the questionnaire are appropriate and adequate to measure pattern and problems of wearing the mouthguard, as well as the general perception on the mouthguard.

Fabrication of mouthguards

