Prior to the fitting of the mouthguard, speech samples will be recorded from each participant. These speech samples were used as control (T₀). The recording of speech samples will be performed using the Sony IC Recorder (ICD-SX700/SX800, San Diego, USA) in a quiet room to minimize background sound. The recorder will be placed 15 cm away from the player's lips and each player will be asked to read loudly a list of selected Malay words (*paku* for phoneme /p/, *bola* for phoneme /b/, *tatu* for phoneme /t/, and *dadu* for phoneme /d/), as the words are shown one after another on the computer screen. Each session will take about 10-20 minutes to complete. Three recordings will be obtained for each word. The mouthguard will then be fitted for each player. The recording of speech samples will be repeated immediately following wear (T₁), and at the following intervals: one-week after (T₂), one-month after (T₃) and six-month after wear (T₄).

Evaluation of oral impairment and compliance

Before the mouthguard is fitted, all participants will be asked to fill up the questionnaires (at T₀). They will also be requested to fill up the same questionnaire at the same time points prior to the recording of the speech samples at T₁, T₂, T₃, and T₄.

Compliance and injury monitoring

Throughout the six-month period, the compliance of wearing mouthguards and the occurrence of dental trauma during training will be monitored on-site by the researcher or if not available, an assigned coach. A 24-hour helpline will be provided as a surveillance tool to monitor problems with mouthguards and dental trauma. Besides, replacement mouthguard will be provided for only once, if the players damage or misplace the mouthguard. However, if the players damage or misplace the mouthguard more than two times, they will be withdrawn from the research.

Data analysis

Data collected from the questionnaires will be analyzed using SPSS version 23.0 (IBM Corporation, Armonk, NY, USA). Descriptive analysis will be performed for demographic data to have an overview of the participants' age, frequency, and duration of playing and experience of wearing a custom-fitted mouthguard.

[figure not shown]

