For the self-assessment questionnaire of oral impairment, Friedman's test will be used to test for differences between groups because the dependent variable being measured is ordinal. Statistical significance is set at $\alpha = 0.05$. Subsequently, the Wilcoxon signed-rank test will be used for pairwise comparison. Bonferroni adjustment will be done to correct for multiple testing. For part (ii) self-reported frequency of wearing custom-fitted mouthguards, comparisons will be made between T₂, T₃, and T₄. Hence, the adjusted level of statistical significance is set at $\alpha = 0.05/3 = 0.017$. For (iii) problems arise during mouthguard use, and (iv) general perception on a mouthguard, the level of statistical significance is adjusted to $\alpha = 0.05/6 = 0.008$ because of multiple testing between T₁, T₂, T₃, and T₄.

All the recorded speech waveforms will be digitized (at a sampling rate of 22 kHz and 32-bit resolution) and stored on a compact disk. The speech samples collected will be transcribed into the PRAAT software version to assess the acoustic characteristics of the sound via spectrographic analysis. Each speech sample file was given a number which referred to a participant's profile to blind the assessor.

By using spectrogram analysis, mean voice onset time (VOT) values for all phonemes */p b t d /* will be measured in a millisecond. The measurements will be done by manually positioning two cursors in the display of the waveform/spectrogram in the sample file. The beginning and end of a particular measurement of a sound will be judged from both the waveform and spectrogram. The average mean VOT values and voicing duration from the three readings will be obtained for each phoneme.

One-way repeated-measures analysis of variance (ANOVA) will be used to compare the VOT of each phoneme at different time intervals (T_0 , T_1 , T_2 , T_3 , T_4). Statistical significance is set at $\alpha = 0.05$.

7. Flowchart of the study

6 month monitoring period

1. Monitoring logbook
2. 24-hour helpline
3. Modification/replacement of mouthguards (if necessary)

Fourth Speech Performance Recording (T₃)

Fourth Questionnaire Oral Impairment Survey
(T₃)

8. References

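### Part (iii) of the questionnaire has no rule for players who have stopped wearing the guard, so their 'Never' answers could read as reduced impairment

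*Combined protocol and SAP*

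**What the plan says.** Objective ii (section 4) is to compare oral impairment across the time points up to six months after wearing the guard.

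- **Scale.** Section 6, on developing the questionnaire, sets one five-point frequency scale for wear and for problems: "The following ratings will be given for the different possible answers in part (ii) and part (iii) with a qualitatively ordinal character", from *Never* = 1 to *Always* = 5. No answer for a player not currently wearing the guard is listed.
- **Who answers.** Section 6, on evaluating oral impairment, says: "Before the mouthguard is fitted, all participants will be asked to fill up the questionnaires". For T1 to T4 it adds: "They will also be requested to fill up the same questionnaire at the same time points prior to the recording of the speech samples". Continued wear is not a condition.
- **Tests.** Under Data analysis: "For the self-assessment questionnaire of oral impairment, Friedman's test will be used to test for differences between groups", followed by Wilcoxon signed-rank tests. For part (iii) the plan states: "For (iii) problems arise during mouthguard use, and (iv) general perception on a mouthguard, the level of statistical significance is adjusted to" 0.05/6 = 0.008, for comparisons among T1, T2, T3 and T4. Part (ii) is compared separately over T2, T3 and T4 at 0.05/3 = 0.017.
- **Compliance.** Section 6 also says "the compliance of wearing mouthguards and the occurrence of dental trauma during training will be monitored on-site by the researcher" or, failing that, a coach. The section 7 flowchart lists a logbook. Neither has a stated role in the analysis of part (iii).
- **Withdrawal.** The only withdrawal rule concerns guards that are repeatedly damaged or lost. It does not cover a player who simply stops wearing his.

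**The concern.** Part (iii) asks how often problems arise during use. For a player who no longer uses the guard the question has no proper answer, and the listed option nearest the truth is *Never*, the most favourable score. A fall in part (iii) between T1 and T4 can then come from players getting used to the guard or from players giving it up. These mean opposite things for objective ii, and the planned tests cannot tell them apart. Because 1 is the floor of the scale, a *Never* from a non-wearer can only lower the later score or leave it unchanged, so any bias favours the guard. The Bonferroni adjustment does not help, because the issue is which answers enter the test.

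Stopping may also be related to the outcome. The Introduction reports that among Malaysian university players "those who discontinued using mouthguard complaint that general discomfort and speech disturbance are the main barriers to compliance".

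**Working it through.** **1. The plan's thresholds.** Four time points give 4 × 3 / 2 = 6 pairs, and 0.05/6 = 0.0083, printed as 0.008. Three time points give 3 pairs, and 0.05/3 = 0.0167, printed as 0.017. Both reproduce.

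**2. What a few non-wearers can do to one test.** Assume 30 players, no change in anyone still wearing the guard, and k players who stop, answer *Never* at T4 and all fall by the same amount. The T1 to T4 Wilcoxon test then has k non-zero differences, all in one direction, and the exact two-sided p is 2/2^k.

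| k stopped | exact p |
|---|---|
| 7 | 2/128 = 0.0156 |
| 8 | 2/256 = 0.0078 |
| 10 | 2/1024 = 0.0020 |

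For k = 8 the tie-corrected normal approximation has variance 8 × 9 × 17/24 − (8³ − 8)/48 = 51 − 10.5 = 40.5. So z = (36 − 18)/√40.5 = 2.83 and p = 0.0047. If every T1 score is 4, the T4 mean is (22 × 4 + 8 × 1)/30 = 3.2. This shows the mechanism only, since real scores vary between visits.

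**3. Simulation with ordinary variability.** None of these assumptions is in the documents except n = 30 and the tests:
- one five-point item, latent correlation 0.5 between visits, no true change from T1 to T4;
- the k most bothered players stop, about half before T3 and the rest before T4, and then answer *Never*;
- no drop-out; 3,000 trials per setting.

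The Wilcoxon tests are two-sided at 0.05/6 and are counted whether or not Friedman's test was significant.

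| Stopped (of 30) | T4 mean | Friedman p < 0.05 | False T1–T4 improvement |
|---|---|---|---|
| 0 | 2.88 | 5% | 0.3% |
| 3 (10%) | 2.56 | 7% | 2% |
| 6 (20%) | 2.28 | 18% | 10% |
| 9 (30%) | 2.03 | 42% | 34% |
| 12 (40%) | 1.81 | 76% | 70% |

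The T1 mean is about 2.88 throughout. With only continuing wearers analysed, Friedman's test rejects in about 4–6% of trials and the false improvement appears in at most 0.5%.

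With 24 players, the number left after the planned 20% drop-out, the false improvement appears in 12% of trials when 6 of 24 (25%) stop and in 29% when 8 of 24 (33%) stop.

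**4. Dependence on who stops.** At 20% stopping, the T4 mean falls by 2.88 − 2.28 = 0.60 when the most bothered stop. If stopping were unrelated to bother, the expected fall would be 0.2 × (2.88 − 1) = 0.38. Selective stopping enlarges the bias but is not needed for it.

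**The case against.** No sentence says that non-wearers' answers are counted. That is inferred from the request to all participants and the absence of any exclusion rule. The questionnaire is still to be developed and pretested, so it may yet carry a skip instruction. This stands as a limit. But a skip would leave gaps, and the plan gives no rule for those either.

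The Introduction goes on to attribute the nuisance largely to poorly fitted stock or boil-and-bite guards, and describes custom-fitted guards as less intrusive. Here national players receive custom-fitted guards, with fit checks, adjustments, on-site monitoring and a helpline. A reader might infer that the worst-affected players here will be the ones who stop and then score best. The documents do not support that: the evidence comes from a different population, using mainly other devices. Stopping may be uncommon, and at 10% the simulated bias is small.

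A reader might also infer that players who wear the guard rarely score at the favourable end. They need not: a player bothered every time he wears it could properly answer *Often* or *Always*. Only complete non-wear clearly produces the problem.

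Finally, part (ii) is compared over T2 to T4, so a large fall in wear could be seen and read alongside part (iii). It would be wrong to say the wear data cannot inform the interpretation. What is missing is a prespecified link.

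**Conclusion.** The point holds as a gap with a definite direction. Following the plan as written, a *Never* from a player who no longer wears the guard can enter the T1 to T4 comparison and read as reduced impairment. The documents give no stopping rate. Under the simulation's assumptions the false T1 to T4 improvement rises from about 2% of trials at 10% stopping to 10% at 20% and 34% at 30%. These figures are illustrative and do not predict this study.

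A reader might conclude that the plan counts players who stop as having adapted. It does not: it has no adapted or not-adapted classification, and the effect is confined to a lower later score. The point concerns part (iii) only. Part (iv) uses an agreement scale about the guard in general, and the voice onset time analysis does not use these answers.

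**What to change.** In the Data analysis section:

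1. State that part (iii) is not applicable, and is not scored as *Never* = 1, at any of T2, T3 or T4 where part (ii) shows the guard is never worn. Name the part (ii) item that decides this.
2. Tabulate part (iii) by part (ii) wear category at each visit.
3. Report the proportion not wearing the guard at each visit beside the wearers' result.
4. Add a sensitivity analysis giving every non-wearer his last score while wearing or, alternatively, the worst score. Applying it to all non-wearers avoids needing a reason for stopping, which the documents do not say is recorded.

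The cost is a few sentences of analysis text, using data already planned. The downside is fewer usable scores at later visits, particularly for Friedman's test, which uses only players with all four scores. The wearers-only result is also selective, so it must be read with the proportion not wearing.

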4. Aim and Objectives

The aim of this study is to evaluate the effect of wearing custom-fitted mouthguards on the speech performance and oral impairment of the Malaysia national rugby players.

The specific objectives are :

- i. To compare the speech performance before, immediately after, one-week after, one-month after and six-month after wearing custom-fitted mouthguard;
- ii. To compare the level of oral impairment before, immediately after, one-week after, one-month after, and six-month after wearing custom-fitted mouthguard; and
- iii. To estimate the incidence of traumatic dental injury within the six-month custom-fitted mouthguards use period.

5. Research hypotheses

The null hypotheses are :

- i. Speech performance at various time points is not affected by wearing custom-fitted mouthguard;
- ii. Level of oral impairment at various time points is not affected by wearing custom-fitted mouthguard; and
- iii. No incidence of dental trauma occurs within the six-month custom-fitted mouthguards use period.

6. Methodology

An interventional study using single-arm pre- and post- design will be carried out at the National Sports Institute. All the national rugby players taking part in the Asia Rugby Championship Premier 2018 will be invited to participate in this study. The information sheet regarding the study will be given out while the objectives and conduct of the study will be explained to the players. All players who agreed to participate will need to provide written informed consent.

To be eligible for inclusion, the players must be:

- a) Men aged between 18 and 35;
- b) Actively playing rugby;
- c) Currently playing in Malaysia Rugby Union;
- d) Native speakers of Malay (national language), with the ability to read and write in Malay fluently;
and
- e) Without any history of either speech or hearing impairment.

The exclusion criteria are:

- a) Retired players;
- b) National players who did not play rugby within the last six months of the recruitment date; and
- c) Players with cleft lip and/or cleft palate; and

d) Players with any history of either speech or hearing impairment.

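### The plan does not state that the VOT assessor is masked to visit, or that files are measured in random order, although VOT is read by hand and compared only across visits

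*Combined protocol and SAP*

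**What the plan says.** Section 6 (Methodology) describes "An interventional study using single-arm pre- and post- design". Under Speech performance measurement, the recordings made before fitting (T0) serve as the control. Recording is repeated immediately after fitting (T1), at one week (T2), at one month (T3) and at six months (T4). Four words are read, and "Three recordings will be obtained for each word".

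Under Data analysis, VOT is obtained by hand: "The measurements will be done by manually positioning two cursors in the display of the waveform/spectrogram in the sample file". The end points are a matter of judgement: "The beginning and end of a particular measurement of a sound will be judged from both the waveform and spectrogram". The three readings are averaged for each phoneme, and "One-way repeated-measures analysis of variance (ANOVA) will be used to compare the VOT of each phoneme at different time intervals".

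The masking provision is a single sentence in the same section: "Each speech sample file was given a number which referred to a participant's profile to blind the assessor". The plan does not mention visit labels or file dates, the order of measurement, who holds the link between number and file, or whether the assessor is a different person from whoever made the recordings.

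**The concern.** There is one arm, so there is no allocation to hide. For the speech outcome the tested contrast is visit, and mainly guard out against guard in. Each player is his own control, so hiding who the player is gives little protection to that contrast. Hiding the visit is what protects it. The sentence on masking names only the participant's profile as the thing the number refers to.

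Two routes to bias stay open on the text as it stands. An assessor who can tell a T0 file from a later one may place cursors slightly differently, without meaning to. Technique may also drift, if files happen to be measured visit by visit over the six months. Either would add to the difference between visits. Averaging three readings reduces random error but leaves a systematic shift untouched, and so does adding players. With no control arm, the analysis cannot separate such an artefact from a real effect of the guard.

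**Working it through.** **Is there a plan figure to reproduce?** None on this point. The protocol gives no VOT standard deviation, cursor error or reader reliability. Masking the visit would not change the sample size. The sample-size paragraph supplies inputs only. (With its stated inputs and six measurements, the standard formula gives 19 players, power 0.820, rather than 24. That is a separate matter and does not bear on this point.)

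**Inputs from the protocol**
- Correlation among repeated measures: ρ = 0.5 (sample-size paragraph).
- Effect size: 0.25, read as Cohen's f (same paragraph).
- n = 24 as the minimum and n = 30 after the dropout allowance (same paragraph).
- Visits: m = 5, the number in the planned ANOVA (T0 to T4).
- α = 0.05 per phoneme (Data analysis).

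**Assumptions not in the protocol**
- Equal SDs at all visits and sphericity.
- No true effect of the guard on VOT.
- A pure measurement shift of d SD between T0 and all four later visits. The values of d are chosen for illustration.

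**Formulas**
- One visit out of five shifted by d gives f² = d² × (1/5) × (4/5) = 0.16 d², so f = 0.4 d.
- Noncentrality: λ = n × m × f² / (1 − ρ) = n × 5 × 0.16 d² / 0.5 = 1.6 n d².
- Degrees of freedom: 4 and 4(n − 1), that is 4 and 92 at n = 24, and 4 and 116 at n = 30.
- Rejection rate: the probability that a noncentral F with parameter λ exceeds the 5% critical value (2.471 at n = 24, 2.450 at n = 30).

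**Results**

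| Shift d (SD) | λ, n = 24 | Rejection, n = 24 | λ, n = 30 | Rejection, n = 30 |
|---|---|---|---|---|
| 0 | 0 | 0.050 | 0 | 0.050 |
| 0.1 | 0.384 | 0.069 | 0.480 | 0.074 |
| 0.2 | 1.536 | 0.135 | 1.920 | 0.161 |
| 0.3 | 3.456 | 0.266 | 4.320 | 0.331 |
| 0.4 | 6.144 | 0.458 | 7.680 | 0.565 |

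**Scale.** If all of the planned f = 0.25 lay between T0 and the rest, it would equal d = 0.25 / 0.4 = 0.625 SD. The shifts in the table are 16% to 64% of that (0.1 / 0.625 and 0.4 / 0.625).

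**Sensitivity to the correlation.** A higher correlation makes the same shift more damaging. At n = 24 and d = 0.2, the rejection rate is 0.135 with ρ = 0.5, 0.202 with ρ = 0.7 and 0.560 with ρ = 0.9.

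**Not modelled.** The table covers a step between T0 and the other visits. Gradual drift in technique would produce a different pattern and was not computed.

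**Volume of files.** 4 words × 3 recordings × 5 visits = 60 per player, and 60 × 30 = 1,800 for 30 players.

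**The case against.** The strongest reply is that the sentence says every file is numbered and gives blinding of the assessor as the purpose. A unique number for each file, with a key leading back to the player's record, fits those words and could hide the visit as well. This stands. A reader might infer that the code identifies only the player and that the assessor will therefore know the visit. The text does not establish either. Nor does it say that files are measured visit by visit. What can be said is that visit masking and measurement order are not stated, and that no other section supplies them.

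Three further objections also limit the point:
- Hiding the player is not worthless. An assessor who recognises a player could anchor a later reading to that player's earlier one. The code should hide both player and visit.
- The questionnaire is also compared across visits, but it is self-reported and the VOT assessor has no part in it. The concern is confined to VOT.
- The shift sizes have no support in the documents, and at 0.1 SD the inflation is small. The rejection rates show what would happen under a given bias, and they are no evidence that such a bias will occur.

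Finally, a guard may change speech audibly, so masking could be incomplete whatever is done. That limits what the fix can achieve, but it is no reason to leave labels and order open. A random order removes drift even when the assessor guesses the visit.

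**Conclusion.** The point holds in a limited form. The stated method does not secure masking of the one contrast on which VOT is tested, and the measurement depends on judgement. Whether bias would follow is unknown. Under the stated assumptions (five visits, correlation 0.5, equal SDs, no true effect, a step between T0 and the rest), a shift of 0.1 to 0.4 SD would raise the per-phoneme false-positive rate from 5% to between 6.9% and 45.8% at n = 24, and to between 7.4% and 56.5% at n = 30. These figures are illustrative, because the documents give no measurement error. The change is worth making because it is cheap and protects the main speech outcome. It would be wrong to report the plan as unblinded.

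**What to change.** Replace the masking sentence under Data analysis with:

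> Each recording (player × visit × word × repetition) receives a random code that reveals neither participant nor visit, with visit labels and file dates removed. All files are measured in one random order mixing players and visits after T4. The key is held by an existing team member other than the assessor until all VOT values are locked.

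If coding of this kind was already intended, the change simply writes it down.

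Cost: a scripted rename and shuffle of about 1,800 files, with no added visits or readings and no change in sample size. Measurement has to wait until the last visit, and an existing team member has to hold the key. Masking may remain incomplete if the guard audibly alters speech, although the random order still removes drift.

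### The VOT analysis is an omnibus repeated-measures ANOVA only: it gives no estimate of change from T0 and, in its standard form, leaves out every recording of a player who misses a visit

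*Combined protocol and SAP*

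**What the plan says.** Section 6 (Data analysis): "One-way repeated-measures analysis of variance (ANOVA) will be used to compare the VOT of each phoneme" at T0, T1, T2, T3 and T4, with significance at 0.05. Nothing further is planned for VOT. For the questionnaire the same section goes on from Friedman's test: "the Wilcoxon signed-rank test will be used for pairwise comparison", with Bonferroni adjustment.

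Section 6 (sample size): "Considering that drop-outs are higher with long-term follow-up, the sample size was increased by 20" per cent, from 24 to 30.

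Section 6 (Speech performance measurement): T0 is recorded before fitting. Then "The recording of speech samples will be repeated immediately following wear" (T1), and again at one week, one month and six months.

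Section 2 (Problem Statement): "It is unclear to what extent speech performance improve over time". Objective i in section 4: "To compare the speech performance before, immediately after, one-week after, one-month after and six-month after wearing custom-fitted mouthguard".

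The document states no analysis population, missing-visit rule or imputation for VOT.

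**The concern.** A one-way repeated-measures ANOVA in its usual form needs a value at every visit, so a player with one missing visit contributes nothing. The plan itself expects losses over six months. T0 and T1 are taken on either side of fitting, so a player who leaves later will normally have both, yet neither would be used. The VOT result would describe only players with all five recordings.

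Separately, and even with no drop-out, a significant omnibus F test says only that the five means are not all equal. It does not say whether VOT shifts at fitting, whether it returns towards T0, or by how many milliseconds. Speech is objective i, and adaptation over time is the gap that the study sets out to fill.

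**Working it through.** **1. Inputs.** From the sample-size paragraph: effect size f = 0.25, alpha 0.05 (reading the 5% margin of error as alpha), power 80%, correlation 0.5, six repeated measurements, minimum 24, final 30. From Data analysis: m = 5 visits. Equal variances and sphericity are assumed unless stated.

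**2. The plan's own figures.** Noncentrality is λ = f²·n·m/(1−ρ), with df (m−1) and (n−1)(m−1). With m = 6, 80% power is reached at n = 19 (0.820; n = 18 gives 0.794). With m = 5 it is reached at n = 21 (0.816). The stated 24 is therefore not reproduced from the stated inputs; that is a separate matter and does not affect this point. The drop-out step does reproduce as an allowance for 20% loss: 24/(1−0.20) = 30, so 30−24 = 6 players.

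**3. Power with 24 completers.** λ = 0.0625×24×5/0.5 = 15, df 4 and 92: power 0.873. With 30 complete players, λ = 18.75, df 4 and 116: power 0.943. Without sphericity, power at n = 24 is 0.809 for epsilon 0.8 and 0.789 for epsilon 0.75. That loss comes from the covariance, not from drop-out.

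**4. Visits left unused, per phoneme, if 6 leave.**

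| Leave after | Recorded | Unused | Share |
|---|---|---|---|
| T1 | 24×5+6×2 = 132 | 12 | 9.1% |
| T2 | 24×5+6×3 = 138 | 18 | 13.0% |
| T3 | 24×5+6×4 = 144 | 24 | 16.7% |

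**5. Precision of T1−T0.** The variance of a within-player difference is 2(1−0.5) = 1 SD². The unadjusted 95% half-width, treating the SD as known, is t/√n:
- n = 24: 2.069/√24 = 0.422 SD
- n = 30: 2.045/√30 = 0.373 SD

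That is about 12% narrower. A simple paired comparison of all 30 players achieves it.

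**6. Precision of T4−T0.** All-available pairs still give n = 24, so no gain. A mixed model borrows from the earlier visits. If the 6 leave after T3, the regression of T4 on T0–T3 has coefficients 0.5/2.5 = 0.2 each and residual variance 1−4×0.5×0.2 = 0.6. The variance of the estimated T4−T0 is then 0.6/24 + 0.40/30 = 0.0383, against 1/24 = 0.0417. The standard error ratio is √(0.0383/0.0417) = 0.959, a gain of about 4%. Leaving after T1 gives 0.0389 and a ratio of 0.966, about 3%.

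**7. Would a mixed-model omnibus test be better?** Simulated trials of 30 players (normal data, correlation 0.5, 6 lost completely at random, one visit mean shifted by 0.625 SD so that f = 0.25, 5,000 runs each) compared an unstructured model with Kenward-Roger inference against the ANOVA on 24 completers:

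| Pattern | Mixed model | ANOVA | ANOVA with Greenhouse-Geisser |
|---|---|---|---|
| Only T1 differs, leave after T3 | 0.900 | 0.874 | 0.854 |
| T0 differs from all later visits, leave after T3 | 0.894 | 0.868 | 0.843 |
| Only T4 differs, leave after T3 | 0.795 | 0.866 | 0.846 |
| Only T1 differs, leave after T1 | 0.875 | 0.871 | 0.849 |

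For an effect at T4 alone the extra visits raise the noncentrality only from 15.0 to 15.1, while the unstructured covariance costs degrees of freedom: Hotelling's test on 24 complete players has power 0.797.

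**8. Why correct the ANOVA.** At n = 24 the simulated type I error (200,000 runs), uncorrected and then with Greenhouse-Geisser, is 5.0% and 3.9% at epsilon 1.00, 6.2% and 4.4% at 0.81, 7.0% and 4.6% at 0.69, and 7.8% and 4.7% at 0.60.

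**The case against.** The case for leaving the plan alone is substantial. The sample was raised to 30 so that 24 would remain, and a complete-case ANOVA is consistent with that. Exclusion of incomplete players is a property of the usual method and is not written in the plan; the statistics package is named only for the questionnaire data. Research question i asks whether there is any difference and objective i is to compare, both of which an omnibus test answers. Missing estimates and missing visits are also two different issues.

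Most of this stands, and it limits the point. A reader might infer that drop-out leaves the study underpowered; step 3 shows that it does not, under the plan's inputs and sphericity. A reader might infer that leaving out drop-outs biases the VOT result. The documents do not show this. The withdrawal rule in section 6 concerns damaged or misplaced mouthguards, not speech. The Introduction does name speech disturbance as a barrier among players who discontinued, but those were university players, and it attributes the nuisance largely to poorly fitted stock or boil-and-bite guards. A reader might also infer that a mixed model should replace the ANOVA as the primary test; step 7 shows that it can do worse for late change.

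What the objection does not answer is the Problem Statement. An omnibus p-value cannot say to what extent VOT changes, and the questionnaire is given follow-up comparisons that VOT is not.

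**Conclusion.** The point holds as a cheap improvement, not as a threat to the study. As written, the plan gives no estimate of VOT change at any visit. If the ANOVA is run on complete cases, 9% to 17% of recorded visits go unused should the 6 allowed drop-outs leave after T1, T2 or T3. The main recoverable gain is at fitting: a T1−T0 half-width of about 0.37 rather than 0.42 SD. For T4−T0 it is nil with available pairs and at most about 4% with a model. These figures rest on the planned correlation of 0.5, equal variances and exactly 6 losses. No claim is made about the presence or direction of bias.

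**What to change.** Add to section 6 (Data analysis), for each phoneme:

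- Keep the repeated-measures ANOVA as the omnibus test, with a Greenhouse-Geisser correction, and state that it uses players with all five recordings.
- Prespecify the mean differences T1−T0, T2−T0, T3−T0 and T4−T0 in milliseconds, with 95% confidence intervals and Holm-adjusted p-values over the four comparisons.
- Base each difference on every player with the relevant visits: either all available pairs, or a mixed model with visit as a categorical effect on all recorded visits. Choose one before analysis.
- Describe T0 and T1 VOT in drop-outs and completers, without a test; about 6 players against 24 is too few for more.

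The cost is SAP wording and a little more analysis, with no new data. Each route has a weakness: the mixed model relies on data being missing at random, and available-pairs differences rest on different players at different visits. An unstructured Kenward-Roger omnibus test should not be made the mandatory primary analysis, because its power falls to about 0.79 if only T4 differs.
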